Clinicaltrials.gov application number: NCT04110314

Title: *Improving Influenza Vaccination Delivery Across a Health System by the Electronic Health Records Patient Portal*

IRB ID17-001889, Amendment 10 for RCT2

Submission Date: 12/14/2017 (RCTs 1-5) **IRB Approval Date:** 12/20/2017

Amendment for RCT2: Approved 10/9/2019

Informed Consent form N/A (approved Waiver of Consent)

RCT2 Protocol (includes statistical analysis plan)

SPECIFIC AIMS

The overall purpose of the RCTs is to evaluate the impact that R/R, delivered through the patient portal, could have on the flu immunization rates of UCLA Health patients. The intent is to ultimately take the information learned and create and disseminate an adaptable toolkit to other health systems.

For RCT #2, we will evaluate the impact of positively framed messages versus negatively-framed messages versus control (standard of care) to see if either type of message has an impact on the receipt of influenza vaccination. The current literature is mixed as to which message type is more effective. The RCT #2 study design will enable us to evaluate the impact in different sub-populations which may demonstrate variability in preference. In addition, RCT #2 will allow us to test the impact of pre-commitment. In the field of behavioral economics, pre-commitment has shown promise as a means of behavior change- in this case, receipt of influenza vaccination. The study design will enable us to evaluate the impact of a pre-commitment question.

Specific Aims for RCT 2:

Aim 1 RCT #2: Using a 3-arm RCT (up to 55 practices), compare the effectiveness of flu reminder recall messages that have been tailored for one of 4 subpopulations- 1) children <18 years, 2) young adults (18-<65 years), 3) older adults (65+ years) and 4) patients with diabetes (identified by SUPREME criteria by CTSI). Within each subpopulation, one arm will receive positively-framed messages highlighting the benefits of flu vaccination, one arm will receive negatively framed messages highlighting the risks associated with not getting the flu vaccine and one arm will serve as the control arm (no portal reminders).

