Aim 2 RCT #2: In addition, we will test the impact of a "pre-commitment" question asking whether the patient plans to receive the flu vaccine (prior to the reminders going out). This question will be asked of half of patients per arm of the 3-arm RCT. Previous research has indicated pre-commitment can improve the likelihood a patient follows through with a behavior. We intend to determine whether pre-commitment increases the likelihood of getting the flu vaccine.

In summary, families will be randomized using a 3x2 factorial allocation (no reminder v. positively-framed reminder v. negatively-framed reminder, and no pre-commitment question v. pre-commitment question). Family members will be divided into 4 non-overlapping cohorts (age <18 years, 18-64 years non-diabetic, 65+ years non-diabetic, and 18+ years diabetic), and a single index member per family per cohort will be selected for inclusion in the study. Only active users affiliated with a UCLA primary care practice will be included in the study sample. For single individuals not part of a family, that individual will serve as the index patient.

Hypotheses:

Hyp 1 RCT #2: Vaccination rates will differ by receipt of no reminders, positively framed reminders and negatively framed reminders.

1.1 Vaccination rates will be higher among patients receiving positively framed reminders than among patients receiving no reminders.

1.2 Vaccination rates will be higher among patients receiving negatively framed reminders than among patients

receiving no reminders.

1.3. Vaccination rates will be higher among patients receiving positively framed reminders than among patients receiving negatively framed reminders.

Hyp 2 RCT #2: Vaccination rates will be higher among patients receiving a pre-commitment question than among patients not receiving the pre-commitment question.

2.1 The arm receiving the pre-commitment question, asking about their intention to get the flu vaccine (prior to the reminders going out), are more likely to follow through with influenza vaccination; therefore, the pre-commitment arm will have higher rates of flu vaccination than the control arm for the pre-commitment component.

The RCT design, subpopulations and letter components have been approved by the MyChart subcommittee, Ambulatory Operations Advisory Group, and the UCLA Health Primary Care Committee.

METHODS AND STUDY PROCEDURES

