* Messages emphasize the benefits of being vaccinated; ** Messages emphasize the risks of not getting vaccinated.

Subject Population

There are approximately n = 430,000 patients in the primary care registry (RCT#2) who are active/inactive portal users and affiliated with the primary care practices of interest for this research. And additional 50,000 meet the SUPREME criteria for diabetes.

Many patients are members of the same family. As such, the research team will assemble family units (using household address, primary telephone number, patient ID of the guarantor, and insurance member ID as the variables of commonality to create these family units). For RCT 2, for each family, 1 individual will be randomly selected as the index patient for each age or diabetic subgroup. Only index patients who are also active portal users and affiliated with a primary care practice (criteria explained below) will have their data analyzed as part of the primary analysis plan.

Secondary analyses will involve all study subjects.

Gender and age: We anticipate the gender distribution to be roughly equal. All ages of patients will be included in the study; however, patient will not receive a message until they are 6 months of age, as the flu vaccine is not recommended for those less than 6 months of age.

Racial and ethnic origin: There are no enrollment restrictions based on race/ethnicity.

Inclusion criteria

A patient at one of the clinics of interest within the UCLA Health System (up to 55 practices). An individual is deemed a primary care patient of the UCLA Health System through the following algorithm:

Assigned managed care patients (UCLAMG) + Attributed patients from other payers/ACOs

≥2 PCP visits in the past 3 years; or

≥1 PCP visit with preventive service code in past 1 year (99381-99397 or G0438/G0439)

All visits cannot be urgent care visits (i.e., excludes visits after hours or on weekends, not by urgent care codes since UCLA does not bill accordingly)

Active patient: We decided to use the algorithm outlined above and currently approved and in place by the UCLA Health System as the research team believes it to be a generalizable model that could be applied to other health systems.

Creating family units

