3. The patient was randomly selected as the index patient in their family unit for one of the age group/diabetic groups

We will assess primary intervention effects among eligible index patients, and secondary analyses for the entire primary care registry since the impact of the intervention reflects the extent of portal penetration and high correlation that exists among members of the same family (up to 480,000 patients for RCT #2, (ISS-generated data extraction: of 430,000; IP-generated data extraction of approximately 50,000 patients meeting the SUPREME criteria for diabetes (MRNS only shared with the study team by the IP group).

Exclusion criteria

Patients will be excluded from the overall study if they are not part of UCLA's primary care registry per the above algorithm detailed in the inclusion criteria.

MEASURES

Dependent Measures

Vaccine Outcome: The primary outcome is influenza vaccination during the vaccination season as measured by analysis of EHR data. For children <9y who had not received prior influenza vaccination, the outcome will be at least 1 influenza vaccination.

Process Outcomes: These will include: (a) total # visits to the practice during the study time period, (b) # flu vaccine or nurse visits, and (c) missed opportunities. Visits will be measured by the EHR, using ICD-10/CPT codes to classify visits to primary care as preventive, acute/chronic, or nurse-vaccination. Missed opportunities are defined as # vaccine-eligible visits during which the patient did not receive an influenza vaccination. These

process metrics will help assess how the intervention worked.

Cost and Cost Effectiveness

Costs: Since the intervention is implemented centrally, we assume no added practice costs. We also assume practice costs/vaccination from portal R/R is identical to standard practice costs/vaccination. We will assess the time and costs of study and implementation personnel and non-personnel costs, distinguishing planning costs from intervention costs. We will measure costs using a standardized time study/resource survey sent weekly to all individuals working on the study that delineates (a) the # hours spent for each individual, and (b) research vs implementation time. We will use national salary estimates by work code from the Bureau of Labor Statistics to value personnel time in standard rates. We will measure non-personnel costs EHR hardware, software, materials.

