RCT 2: Patients in the intervention arms of the RCT will receive up to 4 reminders via the portal, notifying them of a new letter from their provider in the portal system. The letter will include the first name of the patient and the patient's provider name will be added below the signature line. The letter is only accessible to patients once they or their patient proxy (in the case of a patient proxy, typically for young children or elderly patients) log into their UCLA patient portal (password protected). The patient population that received a generic message in RCT #1 is being subdivided into 4 groups (children <18 years, young adults (18-<65 years), older adults (65+ years) and patients with diabetes meeting the SUPREME criteria. A message will only be sent after a child turns 6 months of age (the recommended minimum age for influenza vaccination).

Confidentiality will be maintained with the following procedures:

- 1) any data transfer will occur between entities at UCLA and will involve encrypted mechanisms
- 2) all electronic data will be stored in locked and password protected computers, in locked rooms. Only the statistician will have access to identifiable data.
- 3) All UCLA personnel will complete required CITI and HIPAA courses and training, and all personnel from other institutions will also be required to complete analogous courses and training. Verification of the completion of these trainings must be provided to UCLA personnel upon request.

RISKS TO SUBJECTS

The major risk is one of breach of privacy and confidentiality. We will maintain the strictest of procedures to prevent either of these problems as described above (i.e., staff training, maintaining strict confidentiality of data).

There is always a risk of complications with vaccination, but this study does not vaccinate patients per se -- rather, it reminds patients (or parents of eligible minors) to receive a recommended vaccine and patients should discuss the benefits and risk of influenza and vaccination with their healthcare provider.

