We will employ intent-to-treat analyses using mixed effects log-binomial regression models with practice random effects, an approach recommended for RCTs in which the goal is to estimate the causal effects of interventions on individuals, adjusted for clustering of patients by practice. The primary model terms will be reminder arm (gain-frame v. loss-frame v. none), and pre-commitment arm (prompt v. no prompt). Models will adjust for the following patient characteristics: age, gender, race/ethnicity, primary language, primary payor, and prior receipt of influenza vaccines in the last two years. Evaluation of study hypotheses will be performed using model contrasts, and treatment effects will be reported in terms of risk ratios and 95% CIs. In the event of computational issues, we will replace the log-binomial specification with a log-Poisson specification, and use model-robust standard errors for inference on treatment effect risk ratios.

Additional Analysis

Additional analyses will include evaluation of process measures (e.g., missed opportunities), evaluation of effect modification by patient characteristics, comparison of the gain-frame and loss-frame arms, and evaluation of vaccination receipt including self-reported vaccinations. Process measures will be analyzed similarly to the primary outcome but using different distributions and link functions as appropriate (e.g., negative binomial distributions for number of missed opportunities). Effect heterogeneity will be evaluated by introducing interaction terms into the primary model specification. All secondary analyses will use a significance level of 0.05. All analyses will be performed using SAS v. 9.4 (SAS Institute Inc., Cary, NC).

Process measures: We assessed the percentage of patients who opened the portal reminder letter, as well as the source of influenza vaccination data (health system within UCLA practices, external source via data transfer, patient/proxy update through normal portal processes, or patient/proxy update in response to portal reminders).

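### If updates made in response to portal reminders count as self-reported vaccinations, the reminder-versus-none risk ratios in that additional analysis mix a vaccination effect with a recording effect

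*Combined protocol and SAP*

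**What the plan says.** Under Additional Analysis, the SAP lists "evaluation of vaccination receipt including self-reported vaccinations" among the further analyses and adds: "All secondary analyses will use a significance level of 0.05". The process-measures paragraph that closes the section names four sources of vaccination data. Two are records of doses, from the health system or by external transfer. The other two are "patient/proxy update through normal portal processes, or patient/proxy update in response to portal reminders".

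On exposure, Aim 1 in Specific Aims says "one arm will serve as the control arm (no portal reminders". The RCT 2 paragraph under Privacy and Confidentiality says "Patients in the intervention arms of the RCT will receive up to 4 reminders via the portal". On the second factor, Aim 2 says of the pre-commitment question: "This question will be asked of half of patients per arm of the 3-arm RCT".

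The primary outcome is defined under Dependent Measures: "The primary outcome is influenza vaccination during the vaccination season as measured by analysis of EHR data". For the analysis population, Subject Population states: "Secondary analyses will involve all study subjects".

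Nowhere does the plan say whether both patient/proxy categories, or only one, enter the self-report analysis.

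**The concern.** A patient or proxy who updates the record because a reminder arrived is making a self-report, so the natural reading is that such updates count. A control patient receives no reminder and cannot generate that category. Families are the randomised unit, so a relative's reminder should not supply it either. The self-report outcome would then be ascertained by one more route in the gain-frame and loss-frame arms than in the control arm.

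Suppose a reminder changes nobody's vaccination but leads some people vaccinated at a pharmacy or workplace to say so. In this analysis that would appear as a risk ratio above 1 for gain versus none and for loss versus none, tested at 0.05 and open to being read as a vaccination effect. The direction needs no assumed rate, only that some patients who are already vaccinated and otherwise unrecorded use the route.

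**Working it through.** The documents give no vaccination rate, self-report rate, power or sample size for this analysis, so there is no planned figure to reproduce. What follows illustrates possible sizes. Every rate is assumed.

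**Inputs.** There is no true vaccination effect.
- c = 0.50 of patients have a dose captured by administered or external records.
- u = 0.05 to 0.15 are vaccinated but not captured.
- s = 0.20 of those self-report through normal portal use in every arm.
- r = 0.10 to 0.30 of the remainder report because of a reminder.
- a = share of analysed patients who can be reached by portal. It is 1 if all can, and 0.5 is an assumed share if the analysis takes in all study subjects, some of whom are inactive portal users. Unreachable patients are assumed not to self-report.

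**Formulas.** Recorded rate without reminders: p0 = c + u·a·s. With reminders: p1 = c + u·a·(s + (1 − s)·r). Spurious RR = p1/p0.

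| Case | a = 1 | a = 0.5 |
|---|---|---|
| Low (u 0.05, r 0.10) | 0.514/0.510 = 1.008 | 0.507/0.505 = 1.004 |
| Middle (u 0.10, r 0.20) | 0.536/0.520 = 1.031 | 0.518/0.510 = 1.016 |
| High (u 0.15, r 0.30) | 0.566/0.530 = 1.068 | 0.533/0.515 = 1.035 |

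**A second set of assumptions.** Let 70–90% of true vaccinations be captured, 5% of the rest be reported normally, and 5–20% of those still unrecorded be reported on a reminder. The true rate cancels, and RR runs from 1.005 to 1.080. With 80% captured and 10% responding, RR = 0.829/0.810 = 1.023.

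**Chance of a spurious significant result.** SE(log RR) = sqrt[(1 − p0)/(p0·n) + (1 − p1)/(p1·n)], two-sided 0.05, no covariates. The only cohort-specific count in the documents is about 50,000 patients meeting the diabetes criteria. That is a registry count, not an analysed sample. With equal allocation (assumed), n = 50,000/3 = 16,667 per reminder arm.
- a = 0.5: z = 0.37, 1.46, 3.29, giving 7%, 31%, 91% for low, middle, high. With an assumed design effect of 2 for clustering: 6%, 18%, 64%.
- a = 1, middle: z = 2.93, giving 83%, or 54% with design effect 2.
- At 2,000 per arm, middle: 17% (a = 1) or 8% (a = 0.5).

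**The other contrasts**, middle inputs, a = 1, no true effect.
- Gain versus loss: both arms have the route, so RR = 0.536/0.536 = 1.000 if response is equal. If r is 0.25 in one and 0.20 in the other, RR = 0.540/0.536 = 1.007.
- Pre-commitment: each half averages (0.520 + 0.536 + 0.536)/3 = 0.5307, so RR = 1.000 if the question does not alter self-reporting. If the question itself raised recording in the no-reminder cell to 0.536, RR = 0.536/0.5307 = 1.010.

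**The case against.** Several replies carry weight.

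- **The condition is open.** No sentence says that reminder-response updates count, and the message text is held outside the document, so how such an update is made cannot be checked. This stands, and the point is worded conditionally for that reason. But nothing excludes the source, and including it is the plainer reading.
- **Source by arm may already be planned.** The SAP says process measures will be analysed in the same way as the primary outcome, whose model terms are the two randomised factors, and source of vaccination data sits under process measures. It would therefore be wrong to infer that the plan ignores source by arm. Such a table would expose the imbalance. It would not settle which sources enter the self-report outcome or how its risk ratio should be read.
- **Some reminder-response updates are real extra doses.** They are, and leaving them out loses true effect. The analysis cannot separate them from doses that would have been given anyway, hence a mixture and not pure artefact.
- **It is only an additional analysis.** This stands and limits the severity. A reader might infer that the primary outcome, and so Hypotheses 1.1 and 1.2, is also biased. The documents do not support that: self-reports are named only in the additional analysis, which implies that the EHR-based primary outcome leaves them out, although its definition does not say so expressly.

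**Conclusion.** The point holds as a minor, conditional one. If reminder-response updates are counted, gain versus none and loss versus none in the self-report analysis are biased toward reminders by recording alone. The direction follows from the design; the size cannot be found from the documents. On the assumptions shown, the spurious risk ratio is about 1.004 to 1.080, and the chance of a false positive runs from close to nominal to above 90%. That spread reflects the assumed rates, portal reach and sample size, so the percentages should not be used to argue that a false positive is likely. Doses that reminders truly caused would reduce the bias.

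Two further inferences go too far. One is that reminder-versus-none results from this analysis must be withheld from inference altogether; showing both versions, clearly labelled, is enough. The other is that gain versus loss and pre-commitment are clean. They are free of the problem only if framing and the prompt do not change self-reporting.

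**What to change.** Amend Additional Analysis as follows.

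1. Run the self-report analysis twice, with and without reminder-response updates.
2. Tabulate source of vaccination data by arm, making explicit what the process-measures wording may already cover.
3. Label the version that counts reminder-response updates as recorded vaccination subject to differential ascertainment, and state that it will not be used alone as evidence that reminders raise vaccination.
4. Note that dropping the source may not remove all of the recording effect, since reminders may divert or increase normal portal updates, and that gain-versus-loss and pre-commitment contrasts rest on framing and the prompt not changing self-reporting.

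The cost is SAP wording, one table, and a filter on a variable the study already assesses. The downside is that doses truly caused by a reminder, given elsewhere and known only by self-report, drop out of the restricted version, so it may slightly understate a true effect.
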